1.4 Translational Medicine Objectives

[figure not shown]
- a. To describe the microbiome of the gut in patients undergoing radical cystectomy and urinary diversion prior to initiation of immunonutrition or a nutrition control.
- b. To define the microbiome change in patients undergoing radical cystectomy and urinary diversion after they have received blinded immunonutrition or control nutritional supplement.
- c. To correlate cancer treatments, postoperative complications (specifically infections) and nutritional status with microbiome composition.

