7.3 Radical Cystectomy Surgery

Because blood samples are required to be collected and shipped on Day 2 following surgery (see [Section 15.1](#)), surgery should take place on a Monday, Tuesday, or Wednesday.

a. Antibiotics

The recommended antibiotic protocol is 24 hours of cefoxitin. If the patient has penicillin allergy, gentamicin/clindamycin is an allowable substitution. If another regimen is followed, broad spectrum and enteric coverage should be considered and documented.

b. Considerations

Radical Cystectomy must occur within 1 day after the last ingestion of the drink. Study sites must adhere to the following guidelines adapted from the Enhanced Recovery After Surgery (ERAS) principles to preserve gut function so the patients can continue to take nutrition supplements after surgery.

1. No bowel preparation
2. No nasogastric tubes
3. Prescribe opioid-free pain control or minimize narcotics.
4. Feed study nutrition drinks to patients within 24 hours after surgery.
5. In addition, it is recommended that patients receive alvimopan to avoid opioid-induced constipation.

c. Postoperative hydration

It is recommended that patients receive an intravenous solution of 5% glucose and electrolytes to prevent dehydration until recovery of oral food intake.

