15.2 Specimens for the TM Stool Microbiome (**REQUIRED IF PATIENT CONSENTS**)

The fecal microbiome of patients in a randomized controlled trial of perioperative immunonutrition for reduction of complications following radical cystectomy and urinary diversion.

Stool specimens for translational medicine and banking (submitted to the SWOG Biospecimen Bank – Solid Tissue, Myeloma and Lymphoma Division, Lab #201) are considered optional for the participant.

- a. With patient's consent specimens must be submitted at the time points listed below.
 1. After registration, but before beginning nutritional drink
 2. After nutrition/before surgery (at least 4 days (+/- one drink) of drinks completed)

3. First bowel movement on return to home (+/- 2 days).
- b. Omnipgene-GUT Kit Stool Ordering

Immediately after identifying a patient for the trial, sites must contact SWOG Biospecimen Bank to order Omnipgene-GUT kits via the following URL: <https://kits.bpc-apps.nchri.org>. Orders placed by noon Eastern should be received within 3-4 business days.
- c. Omnipgene-GUT Kit Stool Labeling

Sites will be instructed to label tubes with:

 - SWOG patient number
 - Patient initials
 - Specimen type
 - Collection date

NOTE: The collection date will be filled by the patient on the tube and the Intake Calendar. Sites must verify the date has been added on the tube prior to shipping.
- d. Specimen Collection and Submission Instructions

Collection kits will be sent home with the patients at 2 different times to reduce patient error.

 - (1) 2 kits will be provided after registration for the collection of:
 - After registration, but before beginning nutritional drink
 - After nutrition/before surgery (at least 4 days of drinks completed)
 - (2) 1 kit will be provided after surgery when site staff provides nutritional drinks

Due to the sensitive nature of the collections, patients will collect the specimens at home. Patients must be instructed to bring their specimen back to the site on a subsequent visit.

Site phone calls

- Call the patient at home six days before the surgery date to remind patients to collect their stool sample.
- Call patient prior to 30-day follow-up to bring their samples to appointment.

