Aim 2: The objective of Aim 2 is to assess change in the microbiota between baseline, after nutrition drinks and surgery (post-operative). We will first assess the change using all patients (across both arms). To assess the change in alpha-diversity, the difference in Shannon Index between predrink, pre- and post-operative profiles will be calculated for each individual and compared using a paired t-test at the nominal $\alpha=0.05$ level. Similarly, beta diversity distance matrices will be calculated using the pooled (baseline and post operative) samples to generate a $2n \times 2n$ matrix which will be compared using PERMANOVA with patient

as a stratification variable; 9,999 permutations will be used to generate a p-value with significance called at the $\alpha=0.05$ level.

For individual taxon level analyses (quantified at the genus level), taxa present in less than 15% of samples or with average relative abundance <0.1% will be filtered. Sparsity will be reduced by adding a pseudocount to raw counts or by application of Bayesian-multiplicative replacement. De-sparsified relative abundance data will be center-log-ratios transformed to accommodate compositionality concerns and encourage normality. Subsequently, the change between post- and pre-operative (transformed) data will be calculated for each taxon (on each patient) and the change will be compared using a paired t-test. Benjamini-Hochberg false discovery rate (FDR) will be controlled at the 10% level.

We will repeat the analyses within each arm, separately. Comparisons (in change) across arms will be conducted in Aim 3 (below).

Aim 3: The objective of Aim 3 is to assess the association between microbiome profiles and dichotomous clinical outcomes, including preoperative chemotherapy, post-operative complications, post-operative infections, and post-operative nutritional status. Each outcome will be analyzed separately.

For the primary outcome of post-operative complications, we will assess whether (1) baseline microbiome profiles (2) post-operative microbiome profiles and (3) change in microbiome profiles are associated with post-operative complications.

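### Aim 2's beta-diversity and taxon contrasts all span surgery, so any drink effect is confounded with surgery and antibiotics, although an after-drinks, pre-surgery stool sample is collected

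*Combined protocol and SAP*

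**What the plan says.** Translational objective b (Section 1.4, repeated in 18.9.a) is to define the microbiome change in cystectomy patients "after they have received blinded immunonutrition or control nutritional supplement". The statistical plan widens this: "The objective of Aim 2 is to assess change in the microbiota between baseline, after nutrition drinks and surgery (post-operative").

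Section 15.2 schedules one stool sample for each of those states:

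- Sample 1: "After registration, but before beginning nutritional drink".
- Sample 2: "After nutrition/before surgery (at least 4 days (+/- one drink) of drinks completed").
- Sample 3: "First bowel movement on return to home (+/- 2 days").

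The Aim 2 analyses in 18.9.e use these samples differently:

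- **Shannon index:** predrink, pre-operative and post-operative profiles are all named, with a paired t-test at 0.05.
- **Beta diversity:** "beta diversity distance matrices will be calculated using the pooled (baseline and post operative) samples", forming a 2n x 2n matrix for PERMANOVA stratified by patient.
- **Taxa:** "the change between post- and pre-operative (transformed) data will be calculated for each taxon", tested with a paired t-test and a 10% false discovery rate.

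The analyses are repeated within each arm, and comparison of change across arms is deferred to Aim 3. The Aim 2 power paragraph refers only to change from baseline to post-surgery. On antibiotics, Section 7.3 states: "The recommended antibiotic protocol is 24 hours of cefoxitin".

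**The concern.** Sample 2 is the only one taken after drinks and before surgery. It is what would allow a change seen during the drinks to be separated from a change that follows bowel reconstruction, perioperative antibiotics and a hospital stay. As written, the PERMANOVA leaves it out. The taxon test either leaves it out or uses it as the starting point of an interval that contains the operation.

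A shift in composition or taxa reported under Aim 2 could then come from the drinks, from surgery and antibiotics, or from both, and the specified tests could not tell these apart. Repeating them within each arm keeps the problem. The after-drinks part of Aim 2's own objective would have a diversity result but no composition or taxon result.

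**Working it through.** **Which interval each test sees.** Let d1 be the change from sample 1 to sample 2 (pre-operative drinks only). Let d2 be the change from sample 2 to sample 3 (surgery, prophylaxis, any treatment antibiotics, hospital stay, and normally some or all of the post-operative drinks in Section 7.4).

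- Beta diversity compares samples 1 and 3, the two ends of d1 + d2. The 2n dimension fixes this at two samples per patient.
- The taxon test sees d2 if pre-operative means sample 2. The Shannon sentence suggests this, because it lists pre-operative separately from predrink. It sees d1 + d2 if pre-operative means baseline, which the power paragraph suggests.
- Neither test identifies d1. If the first taxon reading is right, the two tests also start from different samples.

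An illustration for a taxon, in a common SD unit:

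| True d1, d2 | Baseline to post-op (d1 + d2) | Pre-surgery to post-op (d2) | Baseline to pre-surgery (d1) |
|---|---|---|---|
| 0, 0.33 | 0.33 | 0.33 | 0 |
| 0.33, 0 | 0.33 | 0 | 0.33 |
| 0.33, -0.33 | 0 | -0.33 | 0.33 |

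The first two rows look identical from baseline to post-operative. In the third, a real pre-operative change cancels out.

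**Whether Aim 3 fills the gap.** Aim 3 relates baseline, post-operative and change profiles to complications, infection, nutritional status and preoperative chemotherapy. Arm enters as a restriction, an adjustment or an interaction term. No test of change by arm is written, and the after-drinks sample is not named.

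**The plan's power figures.** Inputs from 18.9.e: n = 146 in total and 73 per arm, 80% power, alpha 0.05, and for taxa a 10% FDR with 90% of taxa unchanged. Sidedness is not stated, so two-sided is assumed.

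Paired detectable change = (z for 1 - alpha/2 + z for 0.80) / sqrt(n).

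- Shannon: (1.960 + 0.842) / sqrt(146) = 0.232, and / sqrt(73) = 0.328. With the noncentral t: 0.233 and 0.332. Stated: 0.23 and 0.33.
- Taxa: per-test alpha = 0.1 x 0.1 x 0.8 / (0.9 x 0.9) = 0.0099. The same formula gives 0.283 and 0.400, or 0.286 and 0.410 with the noncentral t. Stated: 0.29 and 0.41.
- Power at the stated values is 78.8% and 79.4% (Shannon) and 81.2% and 80.0% (taxa).

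The figures reproduce. The paired formula depends only on n, alpha and power, so with complete pairs the baseline to pre-surgery contrast has the same detectable changes, each in SDs of its own change score.

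**Contrasts with no stated power.**

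- Between-arm difference in a change score, 73 per arm, two-sided 0.05, 80% power: (1.960 + 0.842) x sqrt(2/73) = 0.46 SD.
- If three pairwise Shannon contrasts share 0.05 by Bonferroni, 0.23/0.33 becomes 0.27/0.39 SD.

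**The case against.** **Surgery is part of the aim.** Objective b concerns patients undergoing cystectomy, and Aim 2 names the post-operative state. Describing change across surgery is legitimate, and neither text promises the change caused by the drinks. This stands, and the surgery-spanning contrasts should stay. It does not account for the after-drinks state that Aim 2 also names.

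**The tests are not blind to the drinks.** A reader might infer that these two analyses measure surgery alone. The documents do not support that. Baseline to post-operative includes the pre-operative drinks, and both possible intervals normally include post-operative drinks. The effect is mixed with surgery, not missing.

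**Baseline to pre-surgery is not a clean answer either.** A reader might infer that it is the one interval able to answer objective b. It covers only the pre-operative half of the regimen. Both arms take a drink, and patients are told at baseline to stop fish-oil supplements (Section 7.1b), so within an arm it is an uncontrolled before-after comparison. This stands, and it is why the between-arm comparison matters.

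**Randomisation could separate the arms even across surgery.** In expectation it balances the operation and planned prophylaxis. That is right, and the plan points to Aim 3 for it, but Aim 3 does not contain it.

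**It may be loose wording.** The beta-diversity sentence follows on from the three-sample Shannon sentence as if parallel. The 2n x 2n matrix and the power paragraph nevertheless favour two samples.

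**Conclusion.** The concern holds in this form: no specified beta-diversity or taxon contrast in Aim 2 separates the pre-operative drinks from surgery and antibiotics, the meaning of pre-operative is unsettled, and the promised between-arm comparison of change is not written. Two of the three Aim 2 analyses are affected. The Shannon analysis is not, although a paired test on three profiles needs its pairs stated.

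A reader might also infer that any surgical shift as large as the plan's detectable change would produce a positive test with no drink effect. The figures do not say that. They give 80% power (average power for taxa), and the 0.23 SD figure belongs to Shannon. Such a shift could produce a positive result. How large it would be is not given in the documents.

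The conclusion assumes the two-sample reading of the PERMANOVA. The detectable changes assume two-sided tests and complete pairs at 146 and 73. Stool is optional (Section 15.2) and the substudy was added while the trial was enrolling (18.9.d), so paired numbers may be smaller. Prophylaxis is a recommendation, so exposure may vary. The point concerns a translational objective only.

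**What to change.** In 18.9.e:

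1. Define pre-operative as one of the Section 15.2 samples and use the term consistently, including in the power paragraph.
2. Add a baseline to after-drinks/pre-surgery contrast for PERMANOVA and for taxa, overall and within arm.
3. Report pre-surgery to post-discharge and baseline to post-discharge separately, labelled as spanning surgery and antibiotics.
4. Write out the SIM-versus-control comparison of change, including baseline to pre-surgery, because within-arm change is uncontrolled.
5. State power for these contrasts: 0.23/0.33 SD (Shannon) and 0.29/0.41 SD (taxa) with complete pairs at 146/73, and about 0.46 SD between arms for a single change score at two-sided 0.05. Note that optional stool may reduce the paired n.

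The cost is plan wording and a few more tests on samples already scheduled for collection, with taxa still under the 10% FDR. If the Shannon pairs share alpha, their detectable change rises as shown in the working.

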5.2 Prior/Concurrent Therapy Criteria

- a. Patients must have completed any neoadjuvant chemotherapy or immunotherapy (intravesical or systemic) \geq 14 days prior to registration and any toxicities resolved to at least Grade 2.
- b. Patients may have a history of radiation therapy. Radiation therapy must have been completed \geq 180 days prior to registration.
- c. Patients may have a history of prior partial cystectomy. Prior partial cystectomy must have been completed at least 180 days prior to registration.
- d. Patients with planned adjuvant chemotherapy within 90 days after radical cystectomy are not eligible.

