Key publications include details on how the microbiome drives key portions of disease and can be modulated with novel therapies. In particular, using 16sRNA sequencing has been established as an association between the gut microbiome and immune modulated diseases in cancer patients, which has led to the identification of novel microbiome-targeted therapeutics. (17)

An additional key publication describes the diversity of the gut microbiome and how the host factors of the microbiome vary between different hosts (different humans with varying diseases) and over time. The presence of more diverse intestinal microbiomes has been correlated with anti-inflammatory properties. (18) This provides insight that the microbiome can be modified by increasing diversification of the microbiome with factors such as nutrition. Importantly the microbial community can be targeted with clinical treatments. (19) For example, one large study found a difference in *C. difficile* infection rates among patients with and without immunonutrition, indicating that there may be advantages to modulating the gut with immunonutrition. (20)

c. Endpoint(s) to be used in analyses:

1. Post Operative complications (any vs. none)
2. Post Operative infections (yes/no)
3. Nutritional status (malnourished vs. adequate nutrition)
4. Other cancer treatments (preoperative chemotherapy vs no preoperative chemotherapy)

d. Experimental approach, validated assays employed and expertise:

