For the baseline analyses (1) and post-operative analyses (2), we will first restrict attention to patients randomized to the specialized immune-modulating nutrition drink arm. Then we will assess the association between alpha diversity (Shannon index) and complications by regressing alpha diversity on indicator for complications and additional covariates. A 1-df test will be used to evaluate the association with complications at the nominal $\alpha=0.05$ level. Beta-diversity analysis will proceed by calculating UniFrac, Bray-Curtis, and Aitchison metrics which will be compared between patients with and without complications using a logistic version of the microbiome regression-based kernel association test (MiRKAT), a generalization of PERMANOVA with improved covariate adjustment, calling significance at the $\alpha=0.05$ level. Finally, transformed taxon abundances (as in Aim 2) will be compared between patients with/without complications by regressing taxon abundance on an indicator for complications, again adjusting for additional covariates. A 1-df test will again be used with FDR controlled at the 10% level.

For baseline and post-operative microbiome samples, we will then repeat these analyses restricting analyses to patients in the control arm and also pooling across arms (with adjustment for arm). Finally, within the pooled analyses, we will further assess whether the microbiome modifies the association between treatment and outcomes. For alpha diversity and individual taxon analyses, we will include two-way interactions between Shannon index or individual taxon abundances, respectively, in the corresponding models and again evaluate significance using a 1-df with FDR controlled at 10%. For beta-diversity analysis, we will embed the distance matrices into kernel metrics (as in MiRKAT), but then we will use a logistic kernel-machine interaction test to assess whether associations between outcome and treatment are heterogeneous by microbiome beta-diversity profiles.

To examine whether change in microbiome profiles is related to preoperative chemotherapy, will conduct similar analyses as in the baseline and post-operative samples, except for alpha diversity and individual taxa, we will, respectively, use change in Shannon Index and change in taxon abundance. For beta-diversity analysis, we will calculate paired analogues of the UniFrac, Bray-Curtis, and Aitchison distances developed by SWOG.

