Following analysis of the primary endpoint, we will repeat the analysis using post-operative complication and infection status and post-operative nutritional status as endpoints instead.

For all analyses, robust and non-parametric alternatives, as well as other data transformations, will be used if statistical assumptions are violated. If necessary, analyses will be adjusted for additional covariates, possibly including: age, BMI, underlying disease (renal disease/etc), sex, baseline nutritional status, preoperative chemotherapy, muscle mass, etc. If necessary, we will also adjust for technical covariates such as storage time and time from surgery to collection (of the post-operative sample). Possible batch effects will be assessed and removed if present per SWOG TM guidelines: the SWOG statistical center has previously validated the use of ComBat (on CLR transformed data) for mitigating batch effects in 16S data.

Sample Size and Power Considerations:

For Aim 1, with a sample size of 73 patients per arm (146 patients, total), we will be able to estimate the prevalence of particular enterotypes or particular bacterial taxa to within 8.1% (95% confidence interval) using all baseline samples.

For Aim 2, we anticipate 80% power to detect a change in alpha-diversity from baseline to post-surgery of 0.23 and 0.33 standard deviations (sds) using all patients and patients in a particular arm, respectively. For individual taxa, conservatively assuming that 90% of taxa do not have change from baseline to post-surgery, then at the FDR=10% level, we anticipate 80% average power to identify a taxon with change in abundance of 0.29 and 0.41 sds, using all patients and patients in an individual arm, respectively.

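### Aim 3 of the microbiome study puts preoperative chemotherapy in scope, but the only chemotherapy model it specifies uses change between samples that all follow chemotherapy

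*Combined protocol and SAP*

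**What the plan says.** Section 1.4(c), repeated in 18.9.a, sets the objective: "To correlate cancer treatments, postoperative complications (specifically infections) and nutritional status with microbiome composition". Section 18.9.c lists as its fourth endpoint "Other cancer treatments (preoperative chemotherapy vs no preoperative chemotherapy".

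Aim 3 in 18.9.e opens by naming four binary variables to be associated with microbiome profiles, each in its own analysis: preoperative chemotherapy, complications, infections and nutritional status. It then does the following:

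- It calls complications the primary outcome and promises three analyses for it: baseline profiles, post-operative profiles and, third, "3) change in microbiome profiles are associated with post-operative complications".
- It writes the baseline and post-operative models on an indicator for complications: first in the immunonutrition arm, then in the control arm, then pooled, and finally with a test of whether the microbiome modifies the treatment–outcome association.
- It begins the change paragraph "To examine whether change in microbiome profiles is related to preoperative chemotherapy", and describes analyses of change in Shannon index, change in taxon abundance and paired beta-diversity distances.
- It continues: "Following analysis of the primary endpoint, we will repeat the analysis using post-operative complication and infection status and post-operative nutritional status".

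Apart from that, chemotherapy appears in the Aim 3 methods only as a covariate that may be added if needed.

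On timing, Section 5.2(a) says "Patients must have completed any neoadjuvant chemotherapy or immunotherapy" at least 14 days before registration. Section 15.2 places the first stool sample "After registration, but before beginning nutritional drink", the second before surgery after at least four days of drinks, and the third at the first bowel movement at home.

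**The concern.** The scope statements and the methods do not match. An analyst following the methods paragraphs would test chemotherapy against change only. One following the opening of Aim 3 would have to choose the sample, the pooling over arms and the model after the fact.

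The change test does not answer objective 1.4(c), which is about composition. Chemotherapy has ended before the first sample, so its effect on the gut flora, if any, is already present at baseline. The part still present later drops out of the difference. A lasting association could therefore be reported as no association. An effect that fades would appear in the change with reversed sign. Study drinks, surgery and perioperative antibiotics fall between the first and last samples, so a positive result would not isolate chemotherapy either.

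**Working it through.** **1. Reading the Aim 3 paragraphs together.** The opening names four variables. Taking out the primary outcome (complications) leaves three to be covered by repetition: chemotherapy, infection and nutritional status. The repeat sentence instead gives complications, infection and nutritional status. The promised third analysis, change against complications, has no paragraph of its own, because the change paragraph names chemotherapy. Exchanging the two terms makes the text coherent, which suggests a drafting swap.

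**2. The plan's own figures.** Aim 3 gives detectable differences in alpha diversity of 0.67, 0.69 and 0.46 SD at 80% power, for complication rates of 42%, 65% and 53% with 73, 73 and 146 patients. Formula (two-sided 0.05 assumed, as sidedness is not stated): d = (1.960 + 0.842) × sqrt(1/n1 + 1/n2).

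- Experimental arm: 30.66 vs 42.34 gives 0.664.
- Control arm: 47.45 vs 25.55 gives 0.688.
- Pooled: 77.38 vs 68.62 gives 0.465.

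With the t distribution the results are 0.674, 0.697 and 0.468. The stated figures reproduce. They all refer to the complications split; none is given for chemotherapy.

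**3. Baseline test of chemotherapy.** The documents give no chemotherapy prevalence, so a range is assumed. With the same formula and 146 donors:

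| Share with chemotherapy | Detectable difference, 80% power |
|---|---|
| 50% | 0.46 SD |
| 40% or 60% | 0.47 SD |
| 30% or 70% | 0.51 SD |
| 20% or 80% | 0.58 SD |

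For an assumed 0.5 SD effect and 73 vs 73, the standard error is sqrt(2/73) = 0.1655 and 0.5/0.1655 = 3.02. Power is Φ(3.02 − 1.96) = Φ(1.06) = 86%.

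**4. Change test of chemotherapy.** Let d be the baseline effect, r the fraction still present at the later sample, and ρ the within-patient correlation. The group difference in change is rd − d = (r − 1)d. The SD of change is sqrt(2(1 − ρ)), which equals 1 at the assumed ρ = 0.5. With d = 0.5 and 73 vs 73:

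| Effect persisting (r) | Difference in change (SD) | Power |
|---|---|---|
| 100% | 0 | 5% |
| 75% | −0.125 | 12% |
| 50% | −0.25 | 33% |
| 25% | −0.375 | 62% |
| 0% | −0.5 | 86% |

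For example, at r = 0.5: 0.25/0.1655 = 1.51, and Φ(1.51 − 1.96) plus a negligible opposite tail is 33%. A simulation of 20,000 trials with t-tests gave about 85% for the baseline test, and 5.2%, 31% and 85% for the change test at r = 1, 0.5 and 0.

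**5. Sensitivity.** At r = 0.5 the change test has 25% power for ρ = 0.3 and 50% for ρ = 0.7. With 30% treated and ρ = 0.5, the baseline test has 79% and the change test 28% at r = 0.5. Stool donation is optional, so 146 is an upper bound. With 100 donors, half treated, the baseline test has Φ(0.5/0.2 − 1.96) = Φ(0.54) = about 71%; the change test remains at 5% for a fully persistent effect.

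**The case against.** The strongest reply is that chemotherapy is in scope. The opening of Aim 3 and the fourth endpoint in 18.9.c both name it, and the opening refers to profiles in general, not only to change. This stands. A reader might infer that the plan excludes a test of chemotherapy against composition, or that objective 1.4(c) gets no usable test. The documents do not support that: the baseline samples, the regression models and MiRKAT are all planned, and only the line connecting them to chemotherapy is missing.

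A reader might also infer that change removes any effect present at baseline. It removes only the part that persists. With drinks, surgery and antibiotics between the first and last samples, full persistence is one extreme, and the 5% at that extreme follows by construction because the true difference in change is zero. At the other extreme, with ρ = 0.5, the change test is as powerful as the baseline test.

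The change test is also legitimate in its own right: it asks whether prior chemotherapy alters the later shift in the microbiome. That is a different question from the one in 1.4(c).

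Finally, the power figures rest on an assumed prevalence, correlation and persistence, and cover only the Shannon index, not the taxon or paired-distance analyses. They are an illustration, not an estimate for this trial.

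What the reply does not cure is the text itself. The general sentence supplies no chemotherapy model, and the paragraphs that do supply one direct the analyst to change.

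**Conclusion.** The point holds as a mismatch between stated scope and specified method. Read literally, the only chemotherapy model in 18.9.e uses change between samples that all follow chemotherapy, while the objective asks about composition. The loss depends on how much of the effect lasts: under the illustrative assumptions above, 86% power at baseline compares with 5% to 86% on change.

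It should be corrected before the microbiome analysis, but its reach is limited. This is an exploratory analysis in an optional stool collection, the plan's stated detectable differences reproduce, and no primary or secondary trial analysis is affected.

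**What to change.** In 18.9.e, Aim 3:

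- (a) Write the change paragraph for post-operative complications, so that it delivers the promised third analysis.
- (b) In the following sentence, list infection, nutritional status and preoperative chemotherapy as the repeat endpoints.
- (c) For chemotherapy, make baseline profiles pooled over both arms the main comparison. That sample precedes the first drink, so the assigned drink cannot have affected it. Keep change as a secondary analysis. Omit the treatment-interaction step, because chemotherapy precedes randomization and cannot be an outcome of the assigned drink.

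It would also help to state a detectable difference for the expected chemotherapy split, alongside those given for complications.

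The cost is wording only. The baseline samples and methods are already planned, and prior neoadjuvant therapy is already recorded as a stratification factor (Section 6.0). That factor covers any neoadjuvant therapy, so the analysis file must separate chemotherapy from immunotherapy.
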